1.4.2 Prior/concomitant medications or therapies

Subjects participating in the trial must be on stable therapy prescribed for CRPS, including any multidisciplinary treatment program (e.g., consisting of physical therapy, occupational therapy, cognitive behavioral therapy, and/or graded motor imagery, including mirror feedback). Initiation of a new interdisciplinary treatment program during the trial is prohibited. Other allowed therapies, such as spinal cord stimulation, may be continued during the trial if they are stable for at least 1 month prior to the start of treatment.

Subjects may continue treatment with allowed concomitant medications, including any stable analgesic regimens consisting of opioids and other analgesics, if they are on a stable, well-defined treatment regimen for at least 1 month before allocation to IMP and are anticipated to be able to maintain the treatment regimen up to and including Visit 8 at a minimum in the opinion of the investigator. A prescribed regimen including an as needed dosing schedule is permitted. A subject who does not take prescription analgesics but does take over-the-counter analgesics is permitted to participate if considered stable and anticipated to be able to continue taking only over-the-counter and non-prescription analgesics up to and including Visit 8 at a minimum. Over-the-counter analgesics must remain stable throughout the trial, up to and including Visit 8 at a minimum. After Visit 10, investigators should assess the further need of concomitant treatment for CRPS, in particular opioids, and evaluate if the dose or frequency of these treatments can be decreased, or if treatment can be stopped completely. Any resulting changes must be documented in the electronic case report form (eCRF). Subjects receiving treatment in Treatment Period B should remain on stable analgesic treatment (including over-the counter analgesics) between Visit 11 and Visit 16.

In the event a subject experiences a severe pain flare related to CRPS, trauma, or other reason, a course of short-acting analgesics, including opioids, may be prescribed for up to 2 weeks. The concomitant medication must be documented in the eCRF and the sponsor or sponsor's representative (i.e., medical monitor) must be notified.

To alleviate the expected flu-like symptoms (acute phase reaction) potentially associated with the first intravenous administration of bisphosphonates, all subjects in both treatment groups must receive oral acetaminophen (paracetamol) starting from approximately 1 hour prior to the first infusion of IMP and then approximately every 6 hours for the 72-hour period after the first infusion in Treatment Period A and Treatment Period B. Commercially available doses of acetaminophen (paracetamol) can be used as available in the country where the trial is performed. However, the total dose of acetaminophen, including any other medications that contain acetaminophen, must not exceed the maximum allowed dose according to the local product information, and not more than 4 g/day, due to acetaminophen's known risks for hepatic toxicity. Non-steroidal anti-inflammatory drugs should not be used to alleviate the symptoms of the acute phase reaction due to their potential to cause acute changes in renal function, which may confound renal safety assessments.

All subjects will be provided with supplemental calcium and vitamin D, starting from Visit 1 and continuing through to the end of the trial. Calcium and vitamin D supplementation are considered standard of care for patients treated with bisphosphonates and other drugs that inhibit bone turnover. An appropriate daily supplement should be provided to subjects (recommended doses are 500 mg/day to 1000 mg/day calcium and approximately 1000 IU/day vitamin D as locally authorized); if a subject is currently taking calcium and vitamin D supplements, these may be continued without need for additional supplementation, provided levels of supplementation are

similar to those recommended above. A combination product of calcium and vitamin D may be used. Subjects with vitamin D below 30 ng/mL (75 nmol/L) should receive higher doses of vitamin D during the Enrollment Period (e.g., 10 000 IU/day for 10 days), to meet the protocol-required vitamin D levels prior to starting treatment at Visit 2 and prior to starting treatment at Visit 11. As repletion of vitamin D to these levels can be difficult, repeated laboratory testing for vitamin D is permitted during the Enrollment Period (up to a maximum of 4 times in 60 days) and between Visit 10 and Visit 11 (up to a maximum of 2 times). High doses of vitamin D should not be continued after the subject reaches vitamin D targets (supplementation should continue at the recommended daily dose of approximately 1000 IU/day).

With regard to the calcium and vitamin D supplements, the investigator should promote compliance by instructing the subject to take the supplements as prescribed and by stating that compliance is necessary for the subject's safety. Subjects should be instructed to contact the investigator if they are unable for any reason to take the supplements as prescribed. When used as daily supplements in this trial, calcium and vitamin D are not to be considered as an IMP or a medical treatment for an adverse event.

1.4.2.1 Forbidden concomitant medications

The following medications are forbidden for the duration of the trial or as specified:

- Any experimental or investigational treatment or therapy.
- High-dose opioid analgesics (greater than 200 mg oral morphine equivalent daily dose) or combinations of opioids and benzodiazepines or any other treatment regimens that may have potential for significant opioid/sedatives side effects and that may be considered unstable or unsafe (according to the judgment of the investigator).
- Concomitant use of drugs with the potential to cause hypocalcemia (e.g., aminoglycosides). Subjects on a stable dose of loop diuretics may be allocated to IMP as long as no dosage increases in the diuretic medication are anticipated and calcium levels are in the reference range.
- Oral, intravenous, or intramuscular bisphosphonates, calcitonin, denosumab, anti-angiogenic drugs or other bone-active drugs (e.g., teriparatide).
- Drugs with risk for torsades de pointes as specified:
 - Drugs with a known risk of torsades de pointes within 7 days prior to allocation and throughout the trial.
 - With the following exceptions: selective serotonin re-uptake inhibitor antidepressants (e.g., citalopram, escitalopram), if QT interval values met entry criteria, subjects were on a stable dose for at least 1 month prior to Visit 1, and doses are expected to stay stable throughout the trial.
- Concomitant administration of non-steroidal anti-inflammatory drugs or any other agents with the potential to interfere with the assessment of potential changes in renal function (e.g., angiotensin converting enzyme inhibitors) until 2 weeks after the last IMP administration per treatment period, unless subjects are receiving a stable dose for at least 1 month prior to Visit 1. Non-steroidal anti-inflammatory drugs should not be used to alleviate the symptoms of the acute phase reaction.

- Use of nerve blocks, ketamine infusions, intravenous immunoglobulin, acupuncture, electromagnetic field treatment, initiation/implementation of radiofrequency ablation or other sympathectomy procedures, or peripheral nerve stimulation, within 6 weeks prior to Visit 1 and for the entire duration of the trial.
- Use of systemic steroids starting 2 weeks prior to Visit 1 and for the entire duration of the trial.

1.5 Statistical analyses

The primary analysis will be performed once all subjects have completed Visit 11 (Week 26), including database lock and unblinding. The results from this 26-week analysis will be reported in an interim integrated clinical trial report.

The final analysis of this trial, including Treatment Period B and Follow-up Period 2, will be performed after the last subject has completed the trial and the database has been locked.

1.5.1 Sample size rationale

The sample size is based on a statistical test of the superiority of 400 mg neridronic acid versus placebo in the primary endpoint. The null hypothesis of no effect, $H_0: 0 \leq \mu_{400} - \mu_0$, is tested against the alternative hypothesis $H_1: \mu_{400} - \mu_0 < 0$. (Note: A pain reduction will be analyzed as a negative change from baseline. An effective treatment will lead to reduced pain and, hence, to a negative mean change from baseline, $\mu < 0$).

For a difference in the means of $\mu_{400} - \mu_0 = -1.0$ points on the NRS, assuming a standard deviation of 2.0 points on the NRS and a 1-sided significance level of 2.5% ($\alpha = 0.025$), 86 subjects per arm will be required to provide at least 90% power ($1 - \beta = 0.9$) to reject the null hypothesis. To compensate for a slight decrease in power due to an optional futility interim analysis, a total of 180 subjects (90 subjects per arm) are planned to be allocated to treatment.

1.5.2 Subject populations

Enrolled Set:	The Enrolled Set includes all subjects who signed the informed consent form.
Allocated Set:	The Allocated Set includes all subjects who are allocated to treatment.
Safety Set:	All subjects with at least 1 IMP administration, including any partial infusion.
Full Analysis Set:	All subjects allocated with at least 1 IMP administration, including any partial infusion.
Pharmacokinetic Set:	All subjects with at least 1 evaluable pharmacokinetic concentration.
Pharmacodynamic Set:	All treated subjects with at least 1 non-missing value for at least 1 of the bone turnover markers.

1.5.3 Statistical methods and analysis

The analysis of primary and secondary efficacy endpoints is described in the subsections below. All other efficacy endpoints will be descriptively summarized in the Full Analysis Set. Confirmatory

testing will be performed for the primary endpoint and for selected secondary endpoints. Further analyses may be done, including statistical hypothesis tests, but all analyses will be exploratory in nature and will not provide confirmatory evidence.

Subject disposition as well as demographic and baseline data and other subject characteristics, e.g., medical history and prior and concomitant medications, will be descriptively summarized for the Full Analysis Set and the Safety Set.

Adverse events, laboratory values, ECG, vital signs, and further safety parameters will be summarized descriptively for the Safety Set. All laboratory parameters will be collected both in SI units and US conventional units. All parameters will be reported in SI units and, in addition, selected laboratory parameters will be reported also in US conventional units (dual reporting).

Pharmacokinetic concentrations will be analyzed in the Pharmacokinetic Set. Descriptive statistics of the observed neridronic acid plasma concentrations at the planned time windows will be created. Owing to the sparse sampling and the random time points, no derivation and analysis of non-compartmental pharmacokinetic parameters is foreseen.

Bone turnover marker values will be descriptively summarized by parameter for the Pharmacodynamic Set.

Health economics and work productivity data will be summarized descriptively for the Full Analysis Set.

Analysis of sIL-2R concentrations will be summarized descriptively for the Safety Set.

All efficacy and safety data evaluated during Treatment Period B and Follow-up Period 2 will be analyzed descriptively separately for subjects who are treated in Treatment Period B and subjects who are not treated. For subjects treated in Treatment Period B, analyses will be performed for subjects initially treated with placebo and subjects initially treated with neridronic acid.

1.5.3.1 Primary endpoint

See Section 1.2 for the definition of the primary endpoint.

For the primary objective of the trial, the primary estimand is the difference in means of the primary efficacy endpoint of 400 mg intravenous neridronic acid compared to placebo for all allocated and treated subjects. This treatment policy or de facto estimand measures the effect of neridronic acid regardless of adherence to treatment or protocol.

The primary estimand will be estimated by the analysis of the primary efficacy endpoint for the Full Analysis Set. The primary analysis will fit a mixed model for repeated measures (MMRM) to the change from baseline in the average pain intensity scores from Week 1 to Week 12 recorded once daily in the electronic diary, including the covariate baseline pain intensity score, and the factors geographic region, week, treatment, and treatment-by-week interaction as fixed effects, and an unstructured covariance matrix to model the covariance structure of the repeated measurements.

The primary efficacy analysis will be performed using the contrast, i.e., the mixed model Wald test, of neridronic acid 400 mg versus placebo at Week 12 of the treatment, week and treatment-by-week interaction term of the mixed effects model described above. Model-based parameter estimates, standard errors, 95% confidence intervals, and p-values will be tabulated. This analysis will be performed using only the observed values without imputation of missing values.

Additional sensitivity analyses will be performed to assess the robustness of primary analysis results. Sensitivity analyses will include the imputation of missing pain intensity scores using different pattern mixture models (PMMs).

A descriptive summary of the weekly averages and the changes from baseline will be generated by treatment group. Graphical displays will be used if appropriate.

1.5.3.2 Secondary efficacy endpoints

All secondary efficacy endpoints will be analyzed for the Full Analysis Set.

Average pain intensity

The change from baseline in the average pain intensity, recorded on the tablet computer, will be analyzed with an MMRM, including the covariate baseline pain intensity score, and the factors geographic region, week, treatment, and treatment-by-week interaction as fixed effects, and subject as random effect. An unstructured covariance matrix will be used to model the covariance structure.

The analysis will be performed using the contrast, i.e., the mixed model Wald test, of 400 mg neridronic acid versus placebo at Week 26 of the treatment, week and treatment-by-week interaction term of the mixed effects model described above. Model-based parameter estimates, standard errors, 95% confidence intervals, and p-values will be tabulated. This analysis will be performed using the observed values without imputation of missing values.

Pain response to treatment

Pain response to treatment, defined as an at least 30% decrease from baseline in average pain intensity, recorded on the tablet computer, will be derived. If a subject shows a worsening or the pain intensity score for the respective visit is missing then the subject will be considered a pain non-responder for the respective visit. A logistic regression model at Week 12 and Week 26 will be fitted to the data, including the covariate baseline pain intensity score, and the factors geographic region, and treatment as fixed effects. Model-based parameter estimates, standard errors, 95% confidence intervals, and p-values for the odds ratio at Week 12 and Week 26 between 400 mg neridronic acid and placebo will be tabulated.

The analysis of pain response to treatment will include a cumulative responder analysis at Week 12, Week 26, and Week 52, where responder rates will be calculated for different percentage thresholds for decrease from baseline in average pain intensity.

Dynamic mechanical allodynia

The change from baseline in the DMA will be analyzed using a similar model as for average pain intensity. Only subjects with allodynia at baseline, i.e., a DMA score greater than 0 on the 0 to 10 NRS, will be included in the analysis.

Pressure pain threshold

The change from baseline in the ratio of the PPT in the affected limb to the PPT in the unaffected limb for the thenar muscle/abductor hallucis muscle will be analyzed using a similar model as for average pain intensity. Only subjects with deep somatic pain (PPT ! 300 kPa) in the affected limb at baseline will be included in the analysis.

Edema

The change from baseline in edema will be analyzed using a similar model as for average pain intensity. Only subjects with presence of the CRPS sign “asymmetric edema” at baseline will be included in the analysis.

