1.2 Trial objectives, endpoints, and outcomes

Objective	Endpoint/Outcome	Measure description and timeframe
Primary	Primary	Primary
To demonstrate the superior efficacy of a cumulative dose of 400 mg intravenous neridronic acid versus placebo for the treatment of CRPS-related pain.	Change from baseline to Week 12 in the average pain intensity score (weekly average of pain values recorded daily in the electronic diary).	11-point numerical rating scale (NRS)—from 0 = “no pain” to 10 = “pain as bad as you can imagine” —reported once daily (in the evening, 24-hour recall) in an electronic diary. The change from the baseline phase (Day -7 to Day -1) to Week 12 will be analyzed.
Secondary	Secondary	Secondary
To assess the efficacy of a cumulative dose of 400 mg intravenous neridronic acid versus placebo for the treatment of CRPS-related pain.	Change from baseline to Week 26 in the average pain intensity recorded on the tablet computer.	11-point NRS—from 0 = “no pain” to 10 = “pain as bad as you can imagine”—reported at the visits on a tablet computer (24-hour recall). The change from baseline (Visit 2 [Day 1]) to Visit 11 (Week 26) will be analyzed.
	Pain response to treatment, defined as at least 30% decrease from baseline in the average pain intensity at Week 12, recorded on the tablet computer.	11-point NRS—from 0 = “no pain” to 10 = “pain as bad as you can imagine”—reported at the visits on a tablet computer (24-hour recall). The change from baseline (Visit 2 [Day 1]) to Visit 8 (Week 12) will be analyzed.
	Pain response to treatment, defined as at least 30% decrease from baseline in the average pain intensity at Week 26, recorded on the tablet computer.	11-point NRS—from 0 = “no pain” to 10 = “pain as bad as you can imagine”—reported at the visits on a tablet computer (24-hour recall). The change from baseline (Visit 2 [Day 1]) to Visit 11 (Week 26) will be analyzed.

Objective	Endpoint/Outcome	Measure description and timeframe
Secondary	Secondary	Secondary

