Collect information for medical resources utilization and health economics ^u		X						X		
Take blood for pharmacokinetic evaluation ^v		X	X	X	X	X				
Take blood for bone turnover marker evaluation ^w		X				X	X	X		X
Take blood for sIL-2R testing		X						X		
Take blood for pharmacogenetic testing ^x		X								
Take blood for omics testing ^x		X						X		
Ask the subject to complete the PGIC							X	X	X	X

a) The Enrollment Period consists of an Enrollment Visit (Visit 1) prior to Day -7 and a baseline pain assessment phase from Day -7 to Day -1 during which subjects will report pain intensity ratings in the electronic diary. These pain intensity ratings will be used to calculate the baseline pain intensity score. Additional visits are allowed during the Enrollment Period to confirm normal laboratory values or ensure protocol targets for vitamin D (for details of repeat testing, see Section 1.3.2). If the Enrollment Period exceeds 30 days, determination of hematology and clinical chemistry parameters should be repeated to confirm there is no major change in the subject's overall health status prior to allocation.

aa) Edema will only be measured in subjects reporting asymmetric edema as part of the assessment of the signs and symptoms of CRPS at baseline (Visit 2). The AROM will only be measured in subjects reporting decreased AROM as part of the assessment of the signs and symptoms of CRPS at baseline (Visit 2).

b) Infusion visits should be separated by 3-day intervals to the extent possible (i.e., Day 1, Day 4, Day 7, and Day 10). Infusion visits on consecutive days are not allowed. The full dosing period must not exceed 21 days from the first infusion (Visit 2). To facilitate scheduling, the interval between infusion visits may be adapted, provided the 21 day time

Grünenthal
Confidential

Protocol KF7013-02 including Amendment 01

Page 23 of 172
DMS version 3.0
20 Nov 2018

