11.1.1.2 Baseline pain assessment phase (Day -7 to Day -1)

In order to calculate the baseline pain intensity score, subjects will be asked to rate their average CRPS-related pain intensity using an 11-point NRS once daily (in the evening) during the last 7 days prior to Visit 2, in the electronic diary. Subjects will also be asked to rate their worst and their current CRPS-related pain intensity once daily during the same period of time. The worst and average pain will be based on a 24-hour recall period.

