**8.2.2 Further definitions**

Baseline	
Baseline is defined as the last observation (scheduled or unscheduled) before first IMP administration if not otherwise specified. In general, baseline is the value recorded at Visit 2.
 
More precisely, for post-baseline comparisons of all parameters except pain intensity in the eDiary, the assessment before first IMP administration at Visit 2 (Day 1) will serve as the baseline based on recorded date/times. In case the value planned on Day 1 is missing or in case there are multiple values before first IMP administration on Day 1, the last scheduled or unscheduled non-missing value before first IMP administration will be used.
 
For current, average, and worst pain, baseline pain intensity will be calculated as the average of the non-missing pain intensity ratings obtained over the 7-day baseline pain assessment phase prior to first IMP administration.

Investigational Medicinal Products (IMP)	The IMPs used in this trial are neridronic acid and matching placebo.
On-treatment-period	For the purpose of this trial, the on-treatment period starts at the first IMP administration (included) and continues until the date (included) when the subject leaves the trial, i.e., at the Final Visit (Visit 17, week 52 after Follow up period 2) for trial completers, and otherwise at the End of Trial date for subjects not fully completing the trial. The on-treatment period extends beyond the dosing period. This is because of the persistence in bone and potentially prolonged effect of neridronic acid.
Pooling of sites	Individual sites will be pooled by geographic region. Geographic regions are defined as USA/Canada, Europe, and Other Regions (including Asia-Pacific and Australia/New Zealand).
Pre-treatment-period	Before the first IMP administration (excluded).
Treatment Period A completers	
Treatment Period A completers are treated subjects who completed IMP administration in Treatment Period A according to the protocol, i.e., subjects who received the full dose of all 4 planned infusions.
 
Subjects are identified via the “Treatment Period A completer” page in the CRF based on the data point “Did the subject complete the treatment?”

Follow-up Period 1 completers	Follow-up Period 1 completers are treated subjects who completed the Follow-up Period according to the protocol, i.e., subjects who have a Visit 11 not before Day 183. Subjects do not need to be Treatment A completers.

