### **13.2.1 Average pain intensity (recorded on tablet computer)**

The change from baseline in the average pain intensity, recorded on the tablet computer, will be analyzed with an MMRM, including the covariate baseline pain intensity score, and the factors geographic region, week, treatment, and treatment-by-week interaction as fixed effects, and subject as random effect. An unstructured covariance matrix will be used to model the covariance structure.

The analysis will be performed using the contrast, i.e., the mixed model Wald test, of 400 mg neridronic acid versus placebo at Week 26 of the treatment, week and treatment-by-week interaction term of the mixed effects model described above. Model-based parameter estimates, standard errors, 95% confidence intervals, and p-values will be tabulated. This analysis will be performed using the observed values without imputation of missing values.

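### The tablet pain models, including the alpha-controlled Week 26 test, do not say which baseline they adjust for, and no reading uses both baselines the trial already collects

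*Protocol*

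**What the plan says.** - **Outcome.** For Week 26 tablet pain, Protocol 1.2 (and SAP 4) states: "The change from baseline (Visit 2 [Day 1]) to Visit 11 (Week 26) will be analyzed".
- **Model.** Protocol 1.5.3.2, repeated in 14.1.7.2, says the change in average pain, "recorded on the tablet computer, will be analyzed with an MMRM, including the covariate baseline pain intensity score". SAP 13.2.1 repeats it: "including the covariate baseline pain intensity score". The logistic responder models in the same protocol sections and in SAP 13.2.2 name the same covariate.
- **Meaning of the term in the protocol.** Footnote a to the schedule in Section 1.7.1 says of the Day -7 to Day -1 diary ratings: "These pain intensity ratings will be used to calculate the baseline pain intensity score". Section 11.1.1.2 opens: "In order to calculate the baseline pain intensity score, subjects will be asked to rate", and goes on to describe once-daily diary ratings. Section 7 ties the term to the same week. The primary diary model uses the identical term, where it can only mean the diary average.
- **Meaning in the SAP.** The second paragraph of the baseline definition in 8.2.2 makes the Visit 2 assessment the baseline for everything except eDiary pain. The third paragraph covers all three pain ratings (average, worst, current) and reads: "baseline pain intensity will be calculated as the average of the non-missing pain intensity ratings obtained over the 7-day baseline pain assessment phase". It does not limit this to the diary. SAP 13.3.1, a descriptive section, takes the Visit 2 value as baseline for tablet pain.
- **Status.** Week 26 tablet pain is one of four secondary endpoints tested under family-wise error control (Protocol 1.5.3.4, SAP 13.2.6). The other three (DMA, PPT ratio, edema ratio) are to be analysed with a similar model, with no covariate named.

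**The concern.** A covariate in a confirmatory test should be identifiable before unblinding. Here two defensible readings give different standard errors and p-values.

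On the literal reading the covariate is the diary average. The model then does not adjust for the value that is subtracted to form the outcome, and the day-to-day noise of one 24-hour rating stays in the change score. On the other reading the covariate is the Visit 2 tablet rating. That is the usual choice, but it leaves out a more reliable seven-day average that inclusion criterion 4 requires for eligibility. At stake is the precision of the 26-week comparison, and an analyst's choice that the plan should have closed.

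**Working it through.** **1. The plan's own figure.** The inputs are in Protocol 1.5.1: difference -1.0, SD 2.0, "a 1-sided significance level of 2.5"%, and "86 subjects per arm will be required to provide at least 90% power". The normal approximation gives 85 per arm. The noncentral t gives power 0.8999 at 85 and 0.9032 at 86, so 86 reproduces. At the planned 90 per arm, power is 0.916. These inputs are for the primary diary endpoint. None is given for tablet pain.

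**2. Diary covariate against tablet covariate.** Let T be the Visit 2 tablet rating, D the 7-day diary mean and Y the Week 26 tablet rating. Assume unit variances, r = corr(Y,T) = corr(Y,D), q = corr(T,D), complete data, and a single-visit approximation to the MMRM. The residual variance of Y - T is:
- given T: 1 - r²
- given D: 2 - 2r - (q - r)²
- difference: (1 - r)² - (q - r)², which is never negative for r ≤ q ≤ 1 and is zero at q = 1.

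Example, r = 0.5 and q = 0.8: tablet 1 - 0.25 = 0.75; diary 2 - 1 - 0.09 = 0.91; ratio 0.91/0.75 = 1.21.

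For power I borrow the primary endpoint's difference of -1.0 and treat 2.0 as the residual SD with the tablet covariate. The SD with the diary covariate is then 2.0 × √ratio. The test is one-sided 2.5% with 90 per arm.

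| r | q | Tablet | Diary | Ratio | Power, diary |
|---|---|---|---|---|---|
| 0.3 | 0.7 | 0.91 | 1.24 | 1.36 | 0.82 |
| 0.5 | 0.7 | 0.75 | 0.96 | 1.28 | 0.84 |
| 0.5 | 0.8 | 0.75 | 0.91 | 1.21 | 0.86 |
| 0.5 | 0.9 | 0.75 | 0.84 | 1.12 | 0.88 |
| 0.5 | 0.95 | 0.75 | 0.798 | 1.06 | 0.90 |
| 0.7 | 0.95 | 0.51 | 0.538 | 1.05 | 0.90 |

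Over r = 0.3 to 0.7 and q = 0.7 to 0.95 the ratio runs from 1.05 to 1.36. Power falls from 0.916 to between 0.90 and 0.82.

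**3. Tablet covariate against both.** Here the diary mean is allowed to be the more reliable measure. Assumed values: true baseline SD 1.5, slope 0.7, Week 26 scatter SD 1.9, single-rating noise SD 1.2. Then:
- Var(T) = 2.25 + 1.44 = 3.69
- Var(D) = 2.25 + 1.44/7 = 2.456
- Cov(T,D) = 2.25
- Var(Y) = 0.49 × 2.25 + 3.61 + 1.44 = 6.1525
- Cov(Y,T) = Cov(Y,D) = 0.7 × 2.25 = 1.575

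Residual variances:
- tablet only: 6.1525 - 1.575²/3.69 = 5.480
- diary only: 6.1525 + 3.69 - 2 × 1.575 - (1.575 - 2.25)²/2.456 = 6.507
- both: 6.1525 - 1.575² × (3.69 + 2.456 - 4.5)/(3.69 × 2.456 - 2.25²) = 5.132

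Ratios: diary/tablet 1.19, diary/both 1.27, tablet/both 1.07.

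**4. Simulation.** Same model, 90 per arm, true baseline mean 6.5, ratings rounded and held to 0-10, diary mean at least 4 at entry, noise SD 0.8 / 1.2 / 1.5. Standard errors from 2,000 trials per level:
- diary only: 0.328 / 0.372 / 0.409
- tablet only: 0.311 / 0.338 / 0.360
- both: 0.305 / 0.328 / 0.350

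Squared ratios for tablet against both are 1.04 / 1.06 / 1.06. A second run of 1,500 trials per level gave 0.313 / 0.350 / 0.368 against 0.311 / 0.339 / 0.359, that is 1.01 / 1.07 / 1.05. This is the source of the 1% to 7%. Diary against tablet is 1.11 / 1.21 / 1.29 in the first run, inside the range of step 2.

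The 1% to 7% belongs to these settings and is not a bound. With the equal correlations of step 2, the variance given both is 1 - 2r²/(1 + q). The tablet/both ratio is then 0.75/0.706 = 1.06 at r = 0.5, q = 0.7, but 0.51/0.424 = 1.20 at the corner r = q = 0.7.

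**The case against.** The strongest reply is that the SAP already points to Visit 2. Its second baseline paragraph covers everything except eDiary pain, and tablet pain is not eDiary pain. The third paragraph can be read as supplying the excepted case, because the 7-day assessment phase is a diary phase. SAP 13.3.1 says Visit 2 outright for tablet pain. The phrase *pain intensity score* is not reserved for the diary either: the responder definition uses it for the tablet rating at a visit. On that reading the model adjusts for the outcome's own baseline, which is ordinary practice, and the remaining loss is small.

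Much of this stands. A reader might infer from the protocol's wording that the tablet models definitely use the diary average. The documents do not support that: it is the literal reading of the term, with SAP text against it. What the reply does not remove is the conflict. The third paragraph is not limited to the diary, 13.3.1 covers descriptive summaries only, and no section names the source of the covariate in the tablet models.

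Adding the diary average is a refinement, as the reply says; its case is that the gain costs almost nothing. For DMA, PPT and edema, a similar model most naturally means the same structure with the endpoint's own baseline. Reading it as adjustment of edema for pain would be strained, so naming the covariate there is clarification only.

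**Conclusion.** The covariate in the tablet pain models is not pinned down, and precision is given up on either reading. If it is the diary average, variance is about 5% to 36% higher than with the tablet rating; the loss is little at a baseline correlation of 0.95 or above and nil at 1. If it is the tablet rating, variance is about 1% to 7% higher than with both baselines in the settings tried.

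These sizes rest on assumed correlations and noise, complete data, a single-visit approximation, and a difference and SD borrowed from the primary endpoint. The power figures are for an unadjusted one-sided 2.5% test, not the gated step-up procedure.

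A reader might infer bias or a false-positive risk. Neither follows: every candidate covariate is measured before treatment in a randomized trial, so the contrast stays unbiased and the type I error intact. The primary endpoint is untouched, because its outcome and covariate are both diary-based. The variance figures do not carry over to the logistic responder models, which are outside the alpha-controlled family.

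**What to change.** 1. In Protocol 1.5.3.2 and 14.1.7.2 and SAP 13.2.1 and 13.2.2, name the Visit 2 tablet average-pain rating as the covariate and add the 7-day diary average as a second covariate.
2. In the third paragraph of the baseline definition in SAP 8.2.2, limit the 7-day rule to diary pain.
3. As a clarification, state in SAP 13.2.3 to 13.2.5 that the covariate is each endpoint's own Visit 2 value (DMA score, PPT ratio, figure-of-eight ratio).

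The cost is wording in both documents before unblinding and one degree of freedom in the tablet models. No new data are needed.
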